- *Maintenance of trough lowering is not a necessary feature of this less frequent arm to test the primary hypothesis. The hypothesis of this 120-mg Q16W arm (acute lowering, followed by more full recovery of target protein) is supported by nonclinical evidence that transient ASO-mediated lowering of HTT protein is associated with sustained phenotypic benefit in the BACHD model (Kordasiewicz et al. 2012). Efficacy in this model is sustained for 6 months even after a complete recovery of target mRNA and protein.*
- Testing the less frequent regimen is of high interest to mitigate potential unknown long-term complications associated with *a more frequent* IT dosing of 120 mg Q8W. This approach could also mitigate the theoretical risks of suppression of wild-type HTT and *will* provide a more patient-friendly long-term dosing regimen.

To date, RO7234292 has only been administered intrathecally in clinical trials. IT bolus administration has been shown to overcome the challenges faced by ASOs, as they are unable to cross the blood-brain barrier and achieve adequate brain and spinal cord concentrations when administered systemically (Schoch and Miller 2017). Therefore, the IT drug delivery method will be used in this trial, as presently no alternatives exist.

A 25-month (2-year) study treatment length has been chosen because the signal-to-noise characteristics of the primary endpoint cUHDRS (TFC for U.S. FDA)—as investigated in prospective observational cohort studies and in placebo groups of prior clinical trials—suggest that this length is optimal for trial *efficacy*. A treatment duration of 25 months will also enable demonstration of sustained, durable benefit on slowing clinical progression as presumed to be achievable with RO7234292 (which is proposed to be administered as a chronic treatment to slow clinical progression). Studies with a shorter treatment duration, such as 18 months, would require a dramatically larger sample size (i.e., 50%) under the 30% slowing of clinical progression assumption. This would result in a potential risk of signal dilution due to inherent variability of a larger number of sites and clinical raters, resulting in a potential increased risk of type II error.

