6.2 DETERMINATION OF SAMPLE SIZE

The planned sample size is adequate to capture meaningful clinical decline on both the TFC and cUHDRS and was estimated on the basis of data available from non-interventional studies (TRACK-HD, COHORT, ENROLL-HD) and a randomized placebo-controlled study (2CARE). Based on these data, using the anticipated trial population, a meta-analysis for the change from baseline at 24 months in TFC score suggested a natural decline of 1.36 points and a corresponding pooled standard deviation of 1.78. A *conservative treatment discontinuation rate at Week 101 for patients receiving placebo or active is assumed to be 20% and 15%, respectively. Using these assumptions, the simulation described below was performed to estimate the sample size.*

Description of Simulations to Derive the Sample Size

The design used for the simulation was simplified to consider only 2 treatment arms (placebo and active) and 2 postbaseline timepoints (Week 49 and Week 101). These simplifications are justifiable given that:

- *A hierarchical procedure will be used to test the primary endpoint for the two regimens against placebo, with the Q8W regimen tested first (see Section 6.3).*
- *The difference on the derived sample size for considering more than two postbaseline timepoints would be minimal.*

The following algorithm was run and repeated 500,000 times:

1. *Generate change from baseline values in TFC at Week 49 and Week 101 for N active patients according to the following bivariate normal distribution:*

$$\begin{pmatrix} y_{wk49} \\ y_{wk101} \end{pmatrix} \sim N \left(\mu = \begin{pmatrix} 0.47 \\ 0.82 \end{pmatrix}, \Sigma = \begin{pmatrix} 1.56^2 & 0 \\ 0 & 1.78^2 \end{pmatrix} \right)$$

where y_{wk49} and y_{wk101} is the change from baseline in TFC, respectively, at Week 49 and Week 101, μ is the assumed true change at those two timepoints, and Σ is the variance-covariance matrix. Subsequently:

- *set to missing, due to study drug-related (SDR) reasons, both values at Week 49 and Week 101 for 5% of the N patients. Set to missing, due to non-study drug-related (NSDR) reasons, both values at Week 49 and Week 101 for additional 2.5% of the N active patients.*
- *set to missing, due to SDR reasons, only the value at Week 101 for additional 5% of the N active patients. Set to missing, due to NSDR reasons, only the value at Week 101 for additional 2.5% of the N active patients.*

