2. Generate change from baseline values in TFC at Week 49 and Week 101 for N placebo patients according to the following bivariate normal distribution:

$$\begin{pmatrix} y_{wk49} \\ y_{wk101} \end{pmatrix} = N \left(\mu = \begin{pmatrix} 0.79 \\ 1.36 \end{pmatrix}, \Sigma = \begin{pmatrix} 1.56^2 & 0 \\ 0 & 1.78^2 \end{pmatrix} \right)$$

where y_{wk49} and y_{wk101} is the change from baseline in TFC, respectively, at Week 49 and Week 101, μ is the assumed true change at those two timepoints, and Σ is the variance-covariance matrix. Subsequently:

- set to missing both values at Week 49 and Week 101 for 10% of the N placebo patients
- set to missing only the value at Week 101 for additional 10% of the N placebo patients

Given how missing data will be imputed, it is not relevant to differentiate missing data into SDR versus NSDR reasons for placebo patients.

3. Apply multiple imputations and derive 20 complete datasets. Missing data on placebo patients were imputed from the placebo arm. Missing data on active patients, depending on if due to NSDR or SDR reasons, were imputed respectively from the active or the placebo arm.
4. Use a t-test to compare active versus placebo at Week 101 for each completed dataset and pool the result (Rubin 1987) to derive an estimate of the treatment effect, including a p-value.

Across the 500,000 simulations, the power achieved, with the N patients per arm was calculated by dividing the number of times the p-value (in above Step 4) was below 5% by 500,000. The above procedure was repeated by only changing the N until the calculated power was close to 80%.

It was estimated that 220 patients per arm will provide approximately 80% power, at a two-sided $\alpha = 0.05$ level, to detect a 40% slowing of clinical decline for RO7234292 as compared with placebo at 101 weeks. This treatment effect translates into an expected average decline of ~0.82 points at 101 weeks for the RO7234292 arms. The minimal detectable difference with these assumptions is ~0.38 points.

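### The sample-size simulation as printed in Section 6.2 gives about 76% power at 220 patients per arm, not approximately 80%; the printed inputs and the stated power need to be reconciled

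*Protocol*

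**What the plan says.** Section 6.2 bases the sample size on TFC and describes a two-arm, two-visit simulation in four steps.

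- **Outcome.** Changes at Weeks 49 and 101 are bivariate normal. Mean declines are 0.79 and 1.36 on placebo and 0.47 and 0.82 on active, with SDs of 1.56 and 1.78. The off-diagonal entries of both covariance matrices are zero.
- **Missing data, active.** The first instruction is: "set to missing, due to study drug-related (SDR) reasons, both values at Week 49 and Week 101 for 5% of the N patients". A further 5% lose Week 101 only for study drug-related reasons. Another 2.5% lose both visits and 2.5% lose Week 101 only for unrelated reasons. The total is 15%.
- **Missing data, placebo.** 10% lose both visits and 10% lose Week 101 only, 20% in total.
- **Imputation.** Twenty datasets are created. For the active arm: "Missing data on active patients, depending on if due to NSDR or SDR reasons, were imputed respectively from the active or the placebo arm". Placebo gaps are filled from placebo.
- **Test.** A t-test at Week 101 in each completed dataset, pooled by Rubin's rules, two-sided 5%.

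The search rule is: "The above procedure was repeated by only changing the N until the calculated power was close to 80" per cent, with 500,000 replicates per run. The result is stated as: "It was estimated that 220 patients per arm will provide approximately 80% power". The section closes with: "The minimal detectable difference with these assumptions is ~0.38 points". The synopsis repeats the power and the minimal detectable difference.

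**The concern.** Because the algorithm is printed in full, it should return the printed answer. It does not appear to: filling 10% of the active arm with placebo-like values dilutes the effect, and the stated 80% looks like what one gets without that dilution. With 500,000 replicates the Monte Carlo standard error near 80% is √(0.8 × 0.2 / 500,000) = 0.06 percentage points, so a search aimed at 80% would not stop at 76% by chance.

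At stake is the stated justification for 660 patients. The same figure underlies the first test in the hierarchy of Section 6.3, where Q16W is tested only if Q8W succeeds. A reader of a non-significant result would judge it against a power that the printed assumptions do not deliver.

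**Working it through.** **1. Inputs (all from Section 6.2).** Difference at Week 101: 1.36 − 0.82 = 0.54 (40% slowing: 0.6 × 1.36 = 0.816, rounded to 0.82). SD 1.78. Between-visit covariance 0. Observed at Week 101 with N = 220: placebo 0.80 × 220 = 176, active 0.85 × 220 = 187.

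**2. What comes near the plan's own figures.**
- Observed patients only, undiluted difference: SE = 1.78 × √(1/176 + 1/187) = 0.187; 0.54/0.187 = 2.89; power = Φ(2.89 − 1.96) ≈ 82%.
- Simple formula inflated for 20% dropout: 2 × (1.960 + 0.842)² × 1.78² / 0.54² gives 171 per arm; 171/0.80 = 214.
- Minimal detectable difference by the usual shortcut: 0.54 × 1.960/(1.960 + 0.842) = 0.378, which rounds to the stated 0.38.

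All three leave out the placebo-based imputation.

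**3. Effect of the printed imputation.** With zero covariance, Week 49 carries no information about Week 101. The 5% + 5% of active patients with drug-related missing values are therefore expected to sit at the placebo mean:

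expected difference = 1.36 − (0.90 × 0.82 + 0.10 × 1.36) = 0.90 × 0.54 = 0.486.

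**4. Simulation of the printed steps.** Regression imputation from the named arm with parameters drawn afresh each time, 20 imputations, pooled-variance t-test, Rubin's rules:

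| Setting | N per arm | Power | Mean estimate | Mean Rubin SE | Critical difference |
|---|---|---|---|---|---|
| As printed (150,000 replicates) | 220 | 76.2% | 0.486 | 0.186 | 0.365 |
| As printed (150,000 replicates) | 240 | 80.0% | 0.486 | 0.178 | 0.350 |
| Barnard-Rubin degrees of freedom (150,000 replicates) | 220 | 75.9% | 0.486 | 0.186 | 0.367 |
| Correlation 0.5 (20,000 replicates) | 220 | 78.8% | 0.495 | 0.184 | 0.361 |
| Correlation 0.7 (20,000 replicates) | 220 | 79.9% | 0.499 | 0.182 | 0.357 |
| Correlation 0.8 (20,000 replicates) | 220 | 80.5% | 0.501 | 0.181 | 0.355 |
| Drug-related gaps imputed from active (20,000 replicates) | 220 | 81.7% | 0.541 | 0.188 | 0.370 |

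The Monte Carlo standard error is 0.1 percentage points with 150,000 replicates and 0.3 with 20,000. Changing only details that the text leaves open (marginal, improper or hot-deck imputation, degrees of freedom, the unrounded active mean 0.816) keeps power between 75.9% and 77.3%.

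**5. Hand check of the 76%.** The estimate behaves like 0.9 times the observed-patient difference, so its sampling SD is about 0.9 × 0.187 = 0.168. Power ≈ Φ((0.486 − 0.365)/0.168) = Φ(0.72) ≈ 76%. At N = 240, with 192 and 204 observed, the SD is 0.9 × 1.78 × √(1/192 + 1/204) = 0.161 and power ≈ Φ((0.486 − 0.350)/0.161) = Φ(0.84) ≈ 80%. Both agree with the simulation.

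**6. Gap.** 80 − 76.2 = 3.8 points. 240/220 = 1.09, that is 9% more patients, or 720 in total instead of 660.

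**The case against.** **The covariance may be the misprint.** Two changes from the same baseline in the same patient would ordinarily be correlated, and there is little reason to simulate Week 49 if it cannot inform the imputation. With a correlation near 0.7 the same algorithm gives about 80% at 220. This stands as a live explanation: in that case N and the power are right and only the matrix is wrong. The text would still need correcting, because no reading of the printed steps was found that reaches 80%.

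**A reader might infer that the trial's type II error is about 24%.** The documents do not support that. The simulation is an acknowledged simplification and uses an unadjusted t-test. Section 6.6.2 plans an ANCOVA with baseline score, CAG repeat length and CAP score. As an assumption only, since no R² is given, covariates explaining 1 − 220/240 ≈ 8% of the variance would make 220 behave like 240. Section 6.6.1 also uses actual off-treatment values after drug-related discontinuation and imputes only what is missing, partly from off-treatment patients in the same arm. Finally, the calculation is for TFC, the primary endpoint for the FDA; elsewhere the primary endpoint is cUHDRS, which was not simulated.

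**A reader might infer that the minimal detectable difference is a second error**, since the simulated critical difference is 0.365. That does not hold: the shortcut gives 0.378 from an undiluted 0.54 and exactly 80% power, which matches the stated value. The protocol does not say on which scale the figure is defined.

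**A reader might set Section 3.3.1 against Section 6.2**, because the former argues "under the 30% slowing of clinical progression assumption". That passage compares an 18-month with a 25-month treatment period. It does not power the trial, and the synopsis and Section 6.2 agree on 40%.

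**Conclusion.** The point holds in a narrow form. The inputs printed in Section 6.2 do not produce the stated power: they give about 76% at 220 per arm, and about 240 per arm would be needed for 80%. The result rests on taking the printed steps literally, including zero covariance and placebo-based imputation for 10% of active patients. It does not depend on how the unspecified imputation details are filled in.

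What is shown is a 3.8-point mismatch between a planning figure and its own stated derivation. Whether the power or an input is misprinted cannot be settled from the protocol, and the mismatch does not establish the power of the planned ANCOVA. It touches neither the estimand nor the type I error.

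**What to change.** Re-run the existing simulation and make Section 6.2 and the synopsis agree with it.

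- If a non-zero covariance, or any other input different from the printed one, was used, print that input together with the power it yields at 220 per arm.
- If the printed inputs are correct, restate the power at 220 per arm as about 76%.
- In either case, say whether the minimal detectable difference of about 0.38 refers to the undiluted treatment effect or to the difference as analysed after imputation. Update it if it was derived by assuming exactly 80% power.

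The cost is a re-run of existing code and a few sentences of text. No change in the number of patients is needed. The one downside, if the inputs prove correct, is a slightly less favourable stated power.

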6.3 TESTING STRATEGY AND MULTIPLICITY ADJUSTMENT

A hierarchical approach will be used for multiple adjustments that accounts for comparisons of two active dosing regimens (RO7234292 Q8W and RO7234292 Q16W) versus placebo, as well as multiple endpoints (the primary and secondary endpoints).

The primary endpoint will be tested for RO7234292 Q8W against placebo at alpha level 5% and, if significant, then RO7234292 Q16W against placebo.

Secondary endpoints will be tested for each active treatment versus placebo. Within each testing chain (RO7234292 Q8W and RO7234292 Q16W), the endpoint will be tested only if the preceding endpoint is significant at the divided alpha level. Details of the order for secondary endpoints and the split of alpha will be detailed in the SAP.

6.4 SUMMARIES OF CONDUCT OF STUDY

The numbers of patients who enroll in the study, discontinue from the study, and complete the study will be summarized overall and by treatment arm. Reasons for premature study withdrawal will be listed and summarized. Enrollment and major protocol deviations will be listed and evaluated for their potential effects on the interpretation of study results.

6.5 SUMMARIES OF DEMOGRAPHIC AND BASELINE CHARACTERISTICS

Demographic and baseline characteristics (including age, sex, CAG repeat length, CAP, HD stage, education) will be summarized using means, standard deviations, medians, and ranges for continuous variables and proportions for categorical variables, as appropriate. Summaries will be presented overall and by treatment group.

6.6 EFFICACY ANALYSES

To ensure the treatment groups under comparison are concurrent and that treatment regimens are comparable across the entire dosing period of the 25-month study, for all efficacy analyses, patients enrolled prior to implementation of Protocol Version 4 will not be included and will be offered the option to enroll into Study BN40955 before reaching the primary endpoint assessment in the current study.

6.6.1 Estimands

Following the very recent estimand framework outlined in the ICH-E9 draft addendum (FDA 2017), the attributes of the estimand for the primary endpoint are defined as follows:

- Population: ITT population (see Section 6.1)
- Variable: Change from baseline in cUHDRS score at Week 101
 - Note: cUHDRS scale will be replaced by TFC scale for the FDA.
- Intercurrent events (ICEs):
 - Treatment discontinued for study drug-related reasons (e.g., treatment-related adverse event or lack of efficacy):

After treatment discontinuation, the actual off-treatment values will be used in the analysis.

- Treatment discontinued for NSDR reasons (e.g., lost to follow-up):

After treatment discontinuation, imputed hypothetical values as if patients had continued receiving study drug will be used in the analysis. In this instance, any data collected after treatment discontinuation will not be included in the analysis.
- Population level summary: Difference in mean change from baseline at Week 101 between each active arm and the placebo arm

The primary estimand is a combination of a treatment-policy strategy and a hypothetical strategy (FDA 2017) to account for the different assumptions for each type of ICE.

The Sponsor will emphasize to investigators the importance of collecting data for the primary endpoint through Week 101, even if patients discontinue study drug but do not withdraw study consent, as well as the importance of providing detailed reasons for treatment discontinuation. The primary estimator, described by the statistical model in Section 6.6.2, will be applied on the dataset produced after multiple imputation of *any missing value*. *In principle*,

- *missing data as well as off-treatment data from patients who discontinued treatment for NSDR reasons will be imputed from patients with available data from the same treatment arm collected while on treatment*
- *missing data from patients who discontinued treatment for SDR reasons will be imputed from:*
 - *patients with available data from the placebo arm collected either while on treatment or off treatment and*
 - *patients with available data from the same treatment arm collected while off treatment*

Multiple imputation of missing data values will be performed as follows:

1. **Imputation step:** *Missing data values will be imputed "m" times leading to "m" complete datasets.*
2. **Analysis step:** *Each of the resulting "m" datasets will be analyzed using the statistical model described in Section 6.6.2, which will provide an estimate of treatment difference.*
3. **Pooling step:** *The results from the "m" datasets will be combined (Rubin 1987) leading to an overall estimate of the treatment effect and associated 95% confidence intervals and p-values.*

Full details of the algorithm for multiple imputation (e.g., *which reference population to use for each missing data pattern, number of imputed datasets, method for imputation, etc.*) will be provided in the SAP.

A supplementary estimand may be considered (and will be defined in the SAP).

6.6.2 Primary Efficacy Analysis

The primary efficacy endpoint is the change from baseline in cUHDRS score at Week 101. This is defined as the attribute "variable" of the primary estimand in Section [6.6.1](#).

Note: The primary efficacy endpoint for the U.S. FDA will be change from baseline in the TFC score at Week 101. TFC will be analyzed the same way as the cUHDRS.

The primary efficacy analysis for this study will compare each active treatment arm, RO7234292 *Q8W* and RO7234292 *Q16W*, against the placebo arm.

To account for the multiple comparison, an appropriate procedure will be used to maintain the overall two-sided type I error at 5% (details will be given in the SAP).

The analysis of the primary endpoint will be performed by means of analysis of covariance (ANCOVA). The model will include the corresponding endpoint baseline score, CAG repeat length, baseline CAP score (defined in Section [4.1.1](#)), and treatment as covariates. On the basis of this analysis, least squares mean for the treatment differences at Week 101 and corresponding 95% CIs will be derived.

The robustness of the primary method of estimation described above may be explored by alternative sensitivity estimators based on varying assumptions underlying the multiple imputation strategy. These sensitivity analyses will be described in the SAP.

6.6.3 Secondary Efficacy Analyses

The secondary efficacy endpoints are identified in Section [2.1.2](#).

Similar hypotheses as for the primary efficacy endpoint will be tested for the secondary continuous efficacy endpoints.

Categorical endpoints, such as CGI-C and the proportion of progressors, will be analyzed by means of logistic regression and will include treatment (categorical), CAG repeat length, and CAP score as covariates.

Methods for controlling type I error in the testing of the secondary endpoints will be described in the SAP.

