6.6.4 Subgroup Analyses

The results of selected efficacy variables will be summarized within subgroups using descriptive statistics. The following variables will be used to define subgroups:

- Sex (male vs. female)
- Age at baseline (< 45 vs. \geq 45 years)
- CAG repeat length (< 43 vs. \geq 43)
- Stage at baseline (I, II, III)
 - Stage III will be considered only if there are enough patients.

Additional exploratory analyses of efficacy results may be performed using an ANCOVA model, similar to the primary analysis, based on change from baseline for the variable of interest, with baseline score (not for analysis by baseline stage), CAP score, CAG repeat length (not for analysis by CAG repeat length), treatment, subgroup, and treatment-by-subgroup interaction as covariates.

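### The logistic models for the TFC and cUHDRS progressor endpoints leave out the baseline score that the ANCOVA of the same scales adjusts for

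*Protocol*

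**What the plan says.** Section 6.6.2 describes the primary ANCOVA, for change in cUHDRS or, for the FDA, in TFC: "The model will include the corresponding endpoint baseline score, CAG repeat length, baseline CAP score", plus treatment. Section 6.6.3 turns to the categorical secondary endpoints, naming CGI-C and the proportion of progressors, and says they "will be analyzed by means of logistic regression and will include treatment (categorical), CAG repeat length, and CAP score as covariates". No baseline score appears in that list.

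Section 2.1.2 defines the progressor endpoints as a TFC decrease of at least 1 point and a cUHDRS decline of at least 1.2 points, both from baseline to Week 101. Section 6.3 puts the secondary endpoints into testing chains, one per active regimen. An endpoint is tested only if the one before it in the chain was significant, at a divided alpha whose split is left to the SAP.

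Section 6.6.3 itself defers only the control of type I error. The synopsis (for the ANCOVA) and Section 6.10 (for the biomarker models) expressly leave the final covariate list to the SAP; Section 6.6.3 has no such sentence.

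**The concern.** A progressor endpoint is a dichotomised change from baseline, so the baseline value is a natural candidate predictor. It is already collected, and the protocol treats it as worth adjusting for when the same change is analysed as a continuous variable. CAG and CAP cannot stand in for it: CAP is age multiplied by CAG length less 33.66 (Section 4.1.1), so neither contains a clinical score. Baseline function may vary widely. Eligibility sets no TFC limit, Section 6.6.4 anticipates Stages I to III, and Section 4.2 names no stratification factor.

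Two things are at stake. If the arms differ by chance at baseline, the ANCOVA corrects for it and the progressor analysis of the same scale does not, so the two can diverge for an avoidable reason. And because testing is sequential, power lost on a progressor endpoint also reduces the chance of reaching whatever follows it in the chain.

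**Working it through.** **Inputs, all from Section 6.2.** "natural decline of 1.36 points and a corresponding pooled standard deviation of 1.78" for placebo; "expected average decline of ~0.82 points at 101 weeks" on active; "220 patients per arm will provide approximately 80% power", with two-sided alpha 0.05; and "treatment discontinuation rate at Week 101 for patients receiving placebo or active is assumed to be 20% and 15%, respectively". The protocol gives no power for the progressor endpoints, no cUHDRS mean or SD, and no correlation between baseline and change. The calculation therefore covers the TFC endpoint only, with the correlation varied from 0 to 0.5.

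**1. The plan's own figure.** The difference is 1.36 − 0.82 = 0.54. Patients per arm for 80% power: 2 × (1.96 + 0.8416)² × 1.78² / 0.54² = 171. Allowing for 20% discontinuation, 171 / 0.80 = 214, within 3% of 220. The inputs are consistent with the stated size.

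**2. Progressor rates implied by those inputs.** Treating the decline as Normal with SD 1.78:
- Placebo: 1 − Φ((1 − 1.36)/1.78) = 1 − Φ(−0.202) = 58.0%.
- Active: 1 − Φ((1 − 0.82)/1.78) = 1 − Φ(0.101) = 46.0%.

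**3. Unadjusted power at 220 per arm.** The difference is 0.1204. The SE is 0.0476 under the null (pooled) and 0.0473 under the alternative. Power = Φ((0.1204 − 1.96 × 0.0476)/0.0473) = 71.6%. With a cut at 0.5, to reflect whole-point scores, the rates are 68.6% and 57.1% and power is 69.9%.

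**4. Logistic regression with and without the baseline score.** Both models contain treatment, CAG and CAP. There are 220 complete patients per arm and 4,000 simulated trials per setting; r is the assumed correlation of baseline with change, given CAP. The Monte Carlo standard error of each power is about √(0.73 × 0.27/4000) = 0.7 points.

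| r | Power without | Power with | log OR (SE) without | log OR (SE) with |
|---|---|---|---|---|
| 0 | 73.3% | 73.2% | −0.502 (0.196) | −0.503 (0.197) |
| 0.1 | 73.0% | 73.3% | −0.503 (0.196) | −0.508 (0.197) |
| 0.2 | 72.9% | 73.8% | −0.503 (0.196) | −0.516 (0.200) |
| 0.3 | 71.0% | 74.2% | −0.496 (0.196) | −0.529 (0.203) |
| 0.4 | 72.6% | 77.0% | −0.504 (0.196) | −0.563 (0.208) |
| 0.5 | 72.4% | 80.1% | −0.501 (0.196) | −0.601 (0.216) |

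The SE rises with adjustment, but the estimate moves away from zero by more. At r = 0.5 the ratio of estimate to SE goes from 0.501/0.1963 = 2.55 to 0.601/0.2159 = 2.78. With the 0.5 cut the gains are similar: 1.4 points at r = 0.2, 2.5 at 0.3, 4.7 at 0.4 and 7.7 at 0.5.

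**5. Type I error.** With no treatment effect, rejection was 5.4% without and 5.3% with baseline at r = 0.3, and 5.6% and 5.4% at r = 0.5.

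**6. The subgroup models of Section 6.6.4, for comparison.** Replacing a continuous covariate by its categories keeps a share k of its explained variance and multiplies the treatment SE by √((1 − k r²)/(1 − r²)). For assumed category shares of 50/50, 60/40 and 10/50/40, k is 0.64, 0.62 and 0.77. At r = 0.3 the SE rises by 1.8%, 1.9% and 1.1%.

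**The case against.** The strongest reply is that nothing here is invalid. Type I error is near 5% either way, randomisation protects the test against chance imbalance on average, and different models for different outcome types are not a contradiction. The opening of Section 6 promises full specification in the SAP, where covariates could still be refined. All of that is fair, and it limits the point to a recommendation. It does not remove it: Section 6.6.3 states the logistic covariates outright, without the deferral used elsewhere for covariate lists.

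The size is also open to challenge. The correlation is not in the protocol, and at 0.2 or below the gain is about nil. The powers assume 220 complete patients and alpha 0.05, whereas Section 6.2 expects discontinuations and Section 6.3 divides alpha for the secondaries. They compare two models and do not state the power of the planned tests. This stands.

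Three stronger readings are tempting, and the documents do not support them.

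- **That the omission costs precision.** In logistic regression a prognostic covariate raises the SE of the log odds ratio, as the table shows, and the adjusted odds ratio is a different conditional quantity. The gain is in power.
- **That CGI-C has the same omission.** CGI-C is rated only after baseline (Section 4.5.9.9), so it has no baseline score to leave out. CGI-S is a separate scale and at best a proxy.
- **That the subgroup ANCOVA in Section 6.6.4 is equally at fault**, being fitted "with baseline score (not for analysis by baseline stage), CAP score, CAG repeat length (not for analysis by CAG repeat length". Those models are optional and exploratory. Stage is a banding of TFC (Section 1.1) and the CAG subgroup is a split of CAG, so each exception avoids entering the same variable twice, while the subgroup factor and CAP stay in. The overlap is only partial when cUHDRS is analysed by stage, but the cost is about 1 to 2% in SE at r = 0.3.

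**Conclusion.** The point holds for the two progressor endpoints. Their models omit an already collected covariate that the protocol uses for the same scales, and no reason is given. Including it gives equal power, within simulation error, or better power at every correlation examined, and corrects chance baseline imbalance. The gain for the TFC endpoint runs from nothing to about 8 points. It rests on an assumed correlation of 0 to 0.5, Normal changes with the Section 6.2 means and SD, complete data and undivided alpha. For cUHDRS the same reasoning applies, but the protocol has no inputs from which to compute a size. This is a low-cost improvement to secondary analyses, not a validity defect, and no primary result depends on it.

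**What to change.** In Section 6.6.3, add the corresponding baseline score to each progressor model: baseline TFC for the TFC endpoint and baseline cUHDRS for the cUHDRS endpoint. For CGI-C, baseline CGI-S (collected at baseline per Appendices 1 and 2) may be added as a proxy and should be labelled as such. Make the change before unblinding and carry it into the SAP. Section 6.6.4 needs no change on this account.

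The cost is a line of wording and no new data. The reported odds ratio becomes conditional on baseline score as well as on CAG and CAP, and the text should say so.
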